Clinical Study Protocol

ProSpective StUdy on DEXTENZA® SafeTy And EffIcacy following coNcomitant MIGS and Cataract Surgery

The SUSTAIN Study

Compound: Sustained Release Dexamethasone,

0.4 mg

IND Number: 146602

NCT: 04200651

Study Name: Prospective Study on DEXTENZA®

Safety and Efficacy following concomitant MIGS and Cataract

Surgery

Clinical Phase: Phase IV open label prospective

Date of Issue: 10/18/2020

Primary Investigator: [name]

Sub Investigator: [name]

Site Name & Location: New York Eye Surgery Center, [name]

CLINICAL STUDY PROT	OCOL SYNOPSIS					
TITLE	Prospective Study on DEXTENZA® Safety and Efficacy following concomitant MIGS and Cataract Surgery					
SITE LOCATION(S)	New York Eye Surgery Center, [name]					
PRINCIPAL	[name]					
Investigator						
Objective(s)	To compare dexamethasone insert to topical corticosteroid use through 90 days in glaucomatous eyes undergoing MIGS and cataract surgery as measured by: visual acuity, IOP control, adverse events, control of inflammation, macular health, and patient comfort.					
STUDY DESIGN	Prospective Fellow-Eye, Randomized Open-label Interventional Study					
STUDY DURATION	Fourteen months, including enrollment period					
ESTIMATED STUDY COMPLETION DATE	February 2022					
POPULATION Sample Size: Target Population:	40 eyes Patients with cataract and glaucoma					
TREATMENT(S) Study Drug	Sustained Release Dexamethasone, 0.4 mg					
Dose/Route/Schedule:	All study eyes will receive cataract extraction, IOL placement, minimally-invasive glaucoma surgery, and a postoperative topical antibiotic prescription. 20 eyes will be randomized to receive Sustained Released Dexamethasone, 0.4 mg. 20 eyes will be prescribed a prednisolone acetate 1% regimen.					
ENDPOINT(S)						
Primary:	 Reduction in IOP at 1 and 3 months BCVA at 1 and 3 months Difference in adverse events between groups Difference in # of glaucoma meds at 3 months 					
Secondary:	 Number of patients requiring supplemental prednisolone acetate 1% eye drops Incidence of CME at 90 days as seen on OCT Difference in Ocular Comfort Index between groups at 1 month and 3 months Difference in % of patients with absence of 					

anterior chamber cells at 30 days between groups

TABLE OF CONTENTS

Clir	nical Stu	dy Protocol Synopsis	2
List	of Table	es	4
1.	Introdu	ction	5
1.1	Type	of study	5
1.2	Introd	luction	5
1.3	Ratio	nale	5
1.4	Purpo	se	6

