1.3 Rationale

Glaucoma and cataract surgery patients face an outsize postoperative burden. In addition to taking frequent anti-inflammatory eye drops, they often continue their glaucoma medications. This can cause patient confusion and nonadherence, potentially leading to poor healing, slower recovery period, and/or cystoid macular edema. DEXTENZA®, as a sustained release anti-inflammatory insert, could help preclude adherence difficulties and increase comfort by reducing eye drop load. However, glaucoma surgeons may hesitate to adopt DEXTENZA® due to concerns regarding safety with respect to elevated intraocular pressure. This prospective study will address those concerns directly, providing timely and high-quality clinical evidence comparing DEXTENZA® to standard-of-care steroid eye drops. For physicians and patients, the results of this study will prove immediately useful for therapeutic decision-making.

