In terms of primary study endpoints, change in IOP values at 1 and 3 months are crucial for quantifying glaucoma outcome differences between groups. We will use three methods to comprehensively assess IOP changes, including Goldmann applanation tonometry, CATS tonometer prism, and the automatic IOP readings provided by the ocular response analyzer. Goldmann is the current standard of care, and thus will be the primary measure. However, CATS tonometry is a valuable supplement because it utilizes a modified prism that may better account for central corneal thickness and corneal hysteresis when providing IOP measurements (McCaffertey et al. 2019). Change in number of glaucoma medications from preop to 3 months postop will be serve as an additional metric to compare glaucoma outcomes. BCVA measurements using an ETDRS chart at 4 meters will indicate whether DEXTENZA® placement in this population affects the visual acuity improvement conferred by an IOL and MIGS. Recording adverse events is necessary not only for the integrity of the study, but also for evaluating the safety of the DEXTENZA® insert for this study population.

supplementary prednisolone acetate 1% eye drops will be recorded to compare ocular inflammation between groups. Checking for absence of anterior chamber cells at 30 days will provide another measure of control of inflammation. Incidence of cystoid macular edema at three months will be used to compare macular health between groups.

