3. STUDY DESIGN

3.1 Study Description and Duration

This prospective, open-label, single-center, randomized, fellow-eye, October 18, 2020 Page 7

investigator-initiated clinical study seeks to investigate the safety and efficacy of the dexamethasone insert in glaucoma patients after concomitant MIGS and cataract surgery. After screening a given patient for inclusion and exclusion criteria, and gaining informed consent, the patient's eligible eye will be randomized to either receive the dexamethasone insert after concomitant cataract-MIGS or to receive prednisolone acetate 1% eye drops after concomitant cataract-MIGS. For participants who enroll only a single eye, block randomization will be performed to ensure that the type of MIGS surgeries will be balanced between the two treatment groups. This stratification is necessary because it is possible that different MIGS devices can confound endpoint measurements, such as IOP control. A stratified block randomization schedule will be developed in advance by the sub-investigator through a computer program, and each assignment will be placed in opaque, sealed envelopes that will be labeled with the stratifying MIGS category. The primary investigator will only open an envelope after a patient is enrolled and the MIGS type that is suitable for the patient is determined. In the few cases where a patient enrolls both eyes, the same MIGS surgery will be performed for each eye. Under such a circumstance, simple randomization will be sufficient to determine whether the first or second eye operated on will receive the dexamethasone insert. The other eye will be placed in the prednisolone acetate 1% eye drops group.

Per enrolled eye, the study period will last for approximately 90 days after surgery, consisting of four postop follow-up visits. At Day 1, Day 7, Day 30, and Day 90, primary and secondary endpoints will be assessed alongside standard-of-care procedures. Adjusting for enrollment period, the study will last a total of approximately twelve months.

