8.2 Primary and Secondary Endpoints

Primary Endpoints

Effect of dexamethasone insert through Day 90 as measured by -

- 1. Mean Reduction in IOP at 1 and 3 months as measured by Goldmann Applanation Tonometer and comparison between groups
- 2. Mean change in ETDRS BCVA at 1 and 3 months and comparison between groups
- 3. Difference in adverse events between the two groups
- 4. Difference in number of glaucoma medications between the wo groups at 3 months

Secondary Endpoints

Through Day 90 as measured by -

- 1. Number of patients requiring supplemental prednisolone acetate 1% eye drops
- 2. Incidence of CME at 90 days as seen on OCT

- 3. Difference in Ocular Comfort Index between the two groups at 1 month and 3 months
- 4. Difference in percentage of patients with absence of anterior chamber cells at 30 days between groups

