9. STATISTICAL PLAN

Primary endpoints and secondary endpoints will be analyzed through statistical hypothesis testing. Demographic and baseline characteristics will be summarized descriptively. Continuous variables will be summarized with mean, median, and standard deviation. Categorical variables will be summarized with frequency and percentage.

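### Primary endpoint 4 (glaucoma medication count at 3 months) depends on unmasked prescribing with no pre-set target IOP or common drop rule, so knowledge of the arm can distort it and, through the drops, endpoint 1; direction and size are not established

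*Combined protocol and SAP*

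**What the plan says.** The synopsis calls the trial a "Prospective Fellow-Eye, Randomized Open-label Interventional Study". Section 3.1 describes sealed, opaque envelopes and says "The primary investigator will only open an envelope after a patient is enrolled" and the MIGS type has been chosen. This conceals the assignment beforehand. No masked prescriber or assessor is described for the period afterwards.

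Section 8.2 lists four primary endpoints. The first is "Mean Reduction in IOP at 1 and 3 months as measured by Goldmann Applanation Tonometer", compared between groups. The fourth is "Difference in number of glaucoma medications between the wo groups at 3 months". Section 1.5 describes the same measure differently, as "Change in number of glaucoma medications from preop to 3 months postop".

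On glaucoma drops during follow-up:

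- Section 1.3 says of these patients that "they often continue their glaucoma medications" after surgery.
- Table 1 (section 5.1) records glaucoma medications and Goldmann IOP at baseline, Day 1, Day 7, Day 30 and 3 months. It also records glaucoma type and severity and the visual field at baseline.
- Section 4.3 leaves medication for other conditions to the physician's discretion.
- Section 5.3 gives rescue criteria based on signs of inflammation only.
- Section 9 says "Primary endpoints and secondary endpoints will be analyzed through statistical hypothesis testing" and does not mention glaucoma drops.

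**The concern.** A medication count measures what was prescribed. When the prescriber knows the arm, the count can reflect that knowledge as well as the treatment. Because many eyes enter surgery on drops and often stay on them, a main discretionary decision is whether to stop an existing drop, and nothing in the protocol guides it.

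The same decision reaches endpoint 1. An unneeded drop raises the count and lowers the IOP reading in the same eye, and section 8.2 states no washout, adjustment or joint analysis. Two of the four primary endpoints therefore share one unguided decision, and they are the two that answer the IOP safety question which section 1.3 says the study will address directly.

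Timing limits the effect. The insert releases drug for up to 30 days (section 4.2.1), so a precautionary drop counts in endpoint 4 only if it is still in use at 3 months. Endpoint 1 is also read at 1 month, when such a drop is more likely to be in use.

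**Working it through.** **Is there a rule?** Sections 4.3, 5.3 and 9 are where one would expect it. All three are present and readable, and none contains a target IOP or criteria for starting, stopping or restarting glaucoma drops. The visit descriptions in 5.2.1 add none.

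**How large could the effect be?** There is no figure of the plan to reproduce: it gives 40 eyes, 20 per arm, without alpha, power, effect size or SD. Only the 20 per arm comes from the documents. Everything else here is assumed:

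- independent eyes, no true difference, two-sided 5% two-sample t-test (38 df, critical value 2.024);
- SD of the medication count 1.0 to 1.3;
- 3 to 5 mmHg IOP lowering per drop (d), and SD of IOP reduction 3 to 5 mmHg;
- a proportion p1 of eyes in one arm and p0 in the other with one unneeded drop in use at the reading.

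Endpoint 4: shift = p1 − p0; variance in each arm = SD² + p(1 − p). 
Endpoint 1: shift = (p1 − p0) × d; variance in each arm = SD² + p(1 − p) × d². 
Non-centrality = shift / √[(var1 + var0)/20]. The false-positive rate is the two-sided rejection probability of the non-central t.

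Worked case, endpoint 4, p1 = 0.25, p0 = 0, SD 1.0: var1 = 1 + 0.1875 = 1.1875 and var0 = 1. Non-centrality = 0.25 / √(2.1875/20) = 0.25 / 0.331 = 0.756, so the rate is 11.4%. With SD 1.3 it is 8.9%.

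| Eyes with an unneeded drop (one arm v other) | Net excess | Endpoint 4 | Endpoint 1 |
|---|---|---|---|
| 10% v 0% | 10 points | 5.6-6.0% | 5.4-7.7% |
| 25% v 15% | 10 points | 5.6-5.9% | 5.4-7.1% |
| 25% v 0% | 25 points | 8.9-11.4% | 7.4-20.8% |
| 40% v 15% | 25 points | 8.7-10.9% | 7.3-18.2% |

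The rows pair up by net excess, so what drives the rate is the difference between arms and hardly the level in either. In 20 eyes, 10 points is 2 eyes on average and 25 points is 5 eyes. The corresponding bias in mean IOP reduction is 0.30-0.50 mmHg at 10 points and 0.75-1.25 mmHg at 25 points.

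The wide range for endpoint 1 comes from its corners. At 25% v 0%, d = 3 with SD 5 gives 7.4%, d = 5 with SD 3 gives 20.8%, and the mid-range case of d = 4 with SD 4 gives 11.4%. The rates are the same whichever arm carries the extra drops.

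**The case against.** **Usual-care discretion may be deliberate.** The insert is indicated for post-surgical inflammation and pain, so the other conditions in section 4.3 could include glaucoma. On that reading discretion was chosen and not overlooked. This is fair, but it only confirms that prescribing is unguided, and the exposure to knowledge of the arm is the same.

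**The data allow partial checking.** Count and IOP are recorded at the same visits and both are primary, so an arm with more drops and lower IOP would show it. This stands in part. The records show what was prescribed. They do not show whether the same eye would have been treated alike in the other arm.

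**Cautious retention would occur in both arms.** This stands. Only the net excess biases the comparison, and the documents give no reason to expect 25 points.

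**One clinician may treat both arms.** The prescriber is not named. If it is the primary investigator alone (an assumption), both arms share that person's habits, but that person still knows the arm.

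Two stronger readings are tempting, and the documents support neither. A reader might infer that the bias runs against the insert, because section 1.3 mentions surgeons' worry about IOP. But section 1.2 expects similar safety and section 6.1 assigns the IOP risk to drops and inserts alike. A reader might also infer that without a recorded target an arm-blind target is lost for good. It is not: baseline IOP, severity, visual field and medications are all collected, and a fixed formula or a masked reader could derive a target from them later. Only the prescribing rule has to be in place beforehand.

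**Conclusion.** The point holds as a gap in design with a modest, conditional effect. Endpoint 4, and through the drops endpoint 1, can be moved by unmasked prescribing that no target or common rule constrains. Analysts cannot supply a prospective prescribing rule afterwards.

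Neither direction nor size can be derived from the documents. Under the assumptions above, a net excess near 10 percentage points hardly matters. Near 25 points the false-positive rate on endpoint 4 roughly doubles, and on endpoint 1 it is about 11% at mid-range values. A reader might take the 25-point figures as an estimate for this trial, but they only illustrate what would have to happen. The calculation treats eyes as independent, which is not exact for patients who enrol both.

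This is a cheap improvement worth making. It does not show that the trial's results would be wrong. Confidence is medium.

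**What to change.** 1. At screening, before the envelope is opened, record a target IOP for each eye, by clinical judgement or by a fixed formula from the baseline data already collected. "In the few cases where a patient enrolls both eyes", record both targets before the first surgery, because the first eye's assignment reveals the second's.
2. State one target-based rule for starting, stopping and restarting glaucoma drops that applies in both arms. Allow departures for safety and record the reason. The stopping part deals with drops kept out of caution.
3. Add one supportive summary by arm: 3-month IOP against target, shown jointly with the change in medication count. It supports endpoints 1 and 4 and does not replace them.

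Separately, align section 8.2 with section 1.5 by defining endpoint 4 as the change from the preoperative count to 3 months. This settles the definition and does nothing about prescribing bias.

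The cost is one extra screening field per eye, slightly narrower prescribing discretion, a recorded reason for each departure, and one summary from data already scheduled. Bias is reduced and not removed: the rule acts on IOP readings for which no masking is described, and departures are decided by someone who knows the arm.

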5. STUDY SCHEDULE OF EVENTS AND VISIT DESCRIPTIONS

5.1 Schedule of Events

Study assessments and procedures are presented by visit in Table 1.

 Table 1
 Schedule of Events

Study Procedure	Screening/ Baseline	Surgica l Visit Day 0	Day 1	Day 7	Day 30	3 MTH post-op	Early Termi nation
Visit	VISIT 1	VISIT 2	VISIT 3	VISIT 4	VISIT 5	VISIT 6	
Windows for Visits	(Day -90 to - 1)		(+/- 2 days)	(+/- 2 days)	(+/- 7 days)	(+/- 14 days)	
Inclusion/Exclusion	X						
Informed Consent	X						
Demographics	X						
Medical History and Concurrent Illnesses	X						
Concomitant Medications (inc. glaucoma meds and supp. prednisolone)	X		X	X	X	X	
BCVA (ETDRS at 4m)	X		X	X	X	X	
Visual field mean deviation	X					X	
Ophthalmic Examination (dilated fundus exam)	X		X	X	X	X	
Cataract density grade (scale 1 to 4) and type	X						
Glaucoma type and severity	X						
OCT RNFL & Macula	X					X	
Intraocular Pressure (Goldmann and CATS)	X		X	X	X	X	
Corneal Endothelial Specular Microscopy	X					X	
Gonioscopy	X					X	
Ocular Response Analyzer	X					X	
Pachymeter	X						
Indirect Ophthalmoscope	X					X	
Indicate the incision type, location, and size (mm)		X					
Type of IOL(e.g. monofocal, toric, multifocal, etc.) and lens power	X	X					
Type of MIGS device	X	X					
Record any surgical complications		X					X
Subject reported AEs prior to or after surgery	X		X	X	X	X	X
Intracanalicular dexamethasone insert		X					
Ocular Comfort Index					X	X	
Anterior chamber cell count			X	X	X	X	
Anterior chamber cell flare			X	X	X	X	
Insert Visualization			X	X	X	X	
Prescribe post-operative topical therapy regimen			X				

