5.3 Rescue Criteria

Rescue criteria include any of the following: moderate to severe photophobia, moderate to severe ciliary or conjunctival injection, or excessive anterior chamber cells or flare.

Rescue treatment would include supplementary prednisolone acetate 1% drops and/or topical NSAIDs, at the discretion of the study doctor.

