6.3 Benefits

For the eye receiving DEXTENZA®, a potential benefit is that the participant will not have to take steroid eye drops in that eye after surgery. DEXTENZA® may potentially be more comfortable and/or convenient than steroid eye drops. The results of this study will benefit future patients by providing clinical evidence comparing the safety and efficacy of DEXTENZA® to steroid eye drops in eyes with glaucoma and a cataract.

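### Secondary endpoint 1 counts only supplemental prednisolone, so an eye rescued with a topical NSAID alone is scored as a non-event in a measure used to compare inflammation

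*Combined protocol and SAP*

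**What the plan says.** Section 8.2 lists as the first secondary endpoint the "Number of patients requiring supplemental prednisolone acetate 1% eye drops". The synopsis has the same endpoint, and neither place mentions NSAIDs.

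Section 1.5 gives its use: "supplementary prednisolone acetate 1% eye drops will be recorded to compare ocular inflammation between groups". The start of that sentence is lost in the text available to us, but the purpose clause is intact. The same paragraph offers absence of anterior chamber cells at 30 days as another measure of inflammation control, which section 2.2 names as a secondary objective.

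Section 5.3 has a single list of rescue triggers (photophobia, injection, cells or flare) and then states: "Rescue treatment would include supplementary prednisolone acetate 1% drops and/or topical NSAIDs, at the discretion of the study doctor". The same triggers can therefore lead to prednisolone, an NSAID, or both.

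Section 3.1 describes the design as "This prospective, open-label, single-center, randomized, fellow-eye". Section 1.5 plans 20 eyes per arm. The schedule in section 5.1 collects "Concomitant Medications (inc. glaucoma meds and supp. prednisolone" at all four postoperative visits. Section 9 promises hypothesis tests and descriptive summaries, and has no rule for handling rescue.

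**The concern.** The endpoint and the rescue rule do not match. An eye that meets a section 5.3 criterion and receives only an NSAID has inflammation that needed treatment, yet it contributes nothing to endpoint 1. This is not a protocol deviation, because the rule as written produces it.

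Two consequences follow. The count understates inflammation needing rescue whenever any rescue is NSAID-only. The between-arm comparison also comes to depend on which drug the doctor picks, and the doctor picks it knowing the arm. Control eyes are already on prednisolone and insert eyes are not, so the choice could differ by arm, although the documents do not show that it does.

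A smaller mismatch sits in the same sentence. The endpoint counts patients, while treatment is allocated by eye. Section 3.1 provides for patients who enroll both eyes ("In the few cases where a patient enrolls both eyes, the same MIGS surgery will be performed for each eye"), with one eye given the insert, and says of the second: "The other eye will be placed in the prednisolone acetate 1% eye drops group". Such a patient belongs to both arms, so a count of patients cannot be assigned to one.

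**Working it through.** **Text check.** Take an eye that meets a section 5.3 criterion and receives an NSAID alone.

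- Section 5.3: a permitted rescue.
- Section 8.2, endpoint 1: not counted, because no supplemental prednisolone was required.
- Section 8.2, endpoint 4 (absence of cells at 30 days): does not count rescue. An eye rescued in the first week may be cell-free by Day 30.
- Section 9: no rule that would bring it back in.

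**Size.** The protocol states no figure that depends on this point, so there is nothing to reproduce. It gives 20 eyes per arm. It gives no rescue rate and no NSAID-only share, so every count below is an assumption.

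Let r be the true rescue rate in an arm and s the share of those rescues that are NSAID-only. Then

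- counted rate = r × (1 − s);
- with equal r in both arms, counted difference (insert minus control) = r × (s_control − s_insert);
- with equal s in both arms, counted difference = (1 − s) × true difference.

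One eye is 1/20 = 5 percentage points. The table subtracts NSAID-only eyes from true rescues; p values are two-sided Fisher exact tests on the counted numbers.

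| True rescues, insert v control | NSAID-only | Counted | True difference | Counted difference | p |
|---|---|---|---|---|---|
| 4 v 4 | 1 v 0 | 3 v 4 | 0 | −5 | 1.00 |
| 4 v 4 | 2 v 0 | 2 v 4 | 0 | −10 | 0.66 |
| 4 v 4 | 0 v 2 | 4 v 2 | 0 | +10 | 0.66 |
| 4 v 4 | 1 v 1 | 3 v 3 | 0 | 0 | 1.00 |
| 5 v 3 | 2 v 0 | 3 v 3 | +10 | 0 | 1.00 |
| 5 v 3 | 0 v 1 | 5 v 2 | +10 | +15 | 0.41 |
| 6 v 2 | 3 v 1 | 3 v 1 | +20 | +10 | 0.61 |

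The fourth row creates no false difference, but each arm's rate reads 15% instead of 20%. In the last row half of the rescues in each arm are NSAID-only, and the 20-point difference is halved: (1 − 0.5) × 20 = 10. The ratio of the two rates stays at 3.

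**Range.** For equal true rescue and an assumed gap between arms of 25 to 50 percentage points in NSAID-only share, the average false difference is:

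- r = 10%: 0.10 × 25 to 0.10 × 50 = 2.5 to 5 points;
- r = 20%: 5 to 10 points;
- r = 30%: 7.5 to 15 points.

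The sign depends on which arm has the larger NSAID-only share. These are expected values. In a trial with 20 eyes per arm the counted difference moves in steps of 5 points, so 2.5 and 7.5 cannot themselves be observed.

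**The case against.** **Added steroid drops are a proper outcome in their own right.** Section 6.3 names as a potential benefit of the insert that "the participant will not have to take steroid eye drops in that eye after surgery", and endpoint 1 measures departures from that. This stands, and the count should be kept. It is incomplete only when read as a measure of inflammation needing rescue, which is the use section 1.5 gives it. The lost opening of that sentence limits certainty about its full wording, but the visible part states the comparison of inflammation.

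**Inflammation is measured in other ways.** Cells and flare are graded at every postoperative visit, and absence of cells at Day 30 is an endpoint. This limits the harm. It does not close the gap, because no endpoint registers an NSAID rescue.

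**No data are lost.** A reader might infer from the schedule, which names supplemental prednisolone and not NSAIDs, that NSAID use goes unrecorded. The documents do not support that. The row is for concomitant medications in general and gives two inclusions, so an any-rescue table could be built. Without a change to the plan, however, that table would not be prespecified.

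**Bias in favour of the insert.** A reader might also infer that an unblinded doctor will choose NSAIDs for insert eyes to spare them steroid drops, and so flatter the insert. The documents give no NSAID-only share in either arm and no direction, and the distortion could equally run the other way. A difference in shares is possible, but it is not shown.

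**Conclusion.** The mismatch is certain from the text: NSAID-only rescue is allowed and is not counted. It follows that inflammation needing rescue is understated whenever such a rescue occurs, and that a real percentage-point difference shrinks if the NSAID-only share is equal in both arms. Distortion of the comparison is conditional on the share differing by arm, which is an inference.

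Each missed eye costs its arm 5 points. Under the assumed counts the counted difference departs from the true one by up to 10 points; the wider assumed range gives an average of up to 15 points, in either direction. None of the worked counts reaches p<0.05, so the harm is to the reported estimate rather than to a claim of significance. One of four secondary endpoints is affected and no primary endpoint changes. The plan should be corrected, but the point does not threaten the trial's main conclusions.

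**What to change.** Leave the rescue rule in section 5.3 as it is. Redefine endpoint 1, in section 8.2 and the synopsis, as the number and percentage of eyes per arm that receive any added anti-inflammatory rescue through Day 90. Added treatment means a new topical NSAID, any prednisolone in an insert eye, or prednisolone beyond the prescribed regimen in a control eye.

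Report two rows beneath it:

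- (a) all supplemental prednisolone, for any reason, with or without an NSAID. This keeps the steroid-drop count that the protocol now defines, by eye. It must not be restricted to section 5.3 triggers, because endpoint 1 carries no such restriction.
- (b) NSAID-only rescue.

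Use the concomitant-medication data already collected at the four postoperative visits, and record the start date and reason for each added drug. Counting eyes also settles the patients-who-enroll-both-eyes problem for this endpoint.

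The cost is the wording change and one small data item, with no new visits. The reported rate may be higher, and the headline moves from steroid drops to any rescue, which is why row (a) stays. The change removes dependence on which rescue drug is chosen. It does not remove the open-label doctor's discretion over whether to rescue.
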